11.3.3.3 Supportive analyses

Supportive/sensitivity analyses will include a model with no adjustment for any baseline characteristics, models adjusting for additional baseline characteristics, subgroup analyses, analysis excluding MRI scans performed within 30 days after treatment with corticosteroids and analyses based on the PPS. Different methods of imputation for subjects with missing lesion counts will be considered in the SAP.

11.3.3.4 Longitudinal change over time in the fatigue related symptoms domain of the FSIQ-RMS from baseline up to EOS

11.3.3.4.1 Hypothesis

FSIQ-RMS-S is a score ranging from 0 to 70 with a higher score indicating more pronounced fatigue. This endpoint will be analyzed using a generalized linear mixed model to account for repeated measures, to compare the overall absolute change in the fatigue score between the two treatment groups. The hypotheses are expressed as a linear combination of the fixed-effects and are tested at a two-sided significance level of 0.05:

$$H_0, \text{FSIQ: } \mu_{\text{Ponesimod}} - \mu_{\text{Placebo}} = 0$$

Vs

$$H_1, \text{FSIQ: } \mu_{\text{Ponesimod}} - \mu_{\text{Placebo}} \neq 0$$

The null-hypothesis will be tested by an F-test.

11.3.3.4.2 Analyses

The primary analysis of change over time in FSIQ-RMS will be performed on the FAS using an adjusted generalized linear mixed model with treatment, time, baseline EDSS category as fixed effect and subject as a random effect. An F-test will be used to compare the overall mean percent change over time in ponesimod compared to placebo. The difference in treatment means and a two-sided 95% CI will also be used to measure the overall treatment effect. The differences at each visit, the effect of time and the interaction between treatment and time will be assessed within the same model. The compound symmetry covariance matrix will be used in the model, however the suitability of this structure will be assessed visually and also compared to an unstructured or autoregressive covariance matrix by assessing the Akaike's information criteria.

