	
for data derivations.
 
Screened analysis set The screened analysis set (SCR) includes all subjects who were screened and received a subject number.
 
Full analysis set The full analysis set (FAS) includes all randomized subjects who were treated with at least one dose of study treatment and have at least one post-baseline efficacy assessment.
 
All primary statistical analyses of efficacy endpoints will be based on the FAS.
 
All-randomized set The all-randomized set includes all randomized subjects.
 
Per-protocol set The per-protocol set (PPS) comprises all subjects included in the FAS without any major protocol deviations.
 
Safety set The safety set (SAF) includes all subjects who received at least one dose of study treatment. Subjects will be analyzed based on actual treatment taken.
 
Primary endpoint variable The primary endpoint is the ARR defined as the number of confirmed relapses per subject-year. All confirmed relapses up to the EOS will be included in the analysis.
 
Secondary endpoint variables There are five secondary efficacy endpoints, which will be analyzed in a hierarchical manner:
 
• Time to 12-week CDA from baseline up to EOS;• Time to first confirmed relapse up to EOS;• Mean number of CUALs per subject per post-baseline MRI scan from baseline up to EOS;• Longitudinal absolute change over time in fatigue-related symptoms as measured by the symptom domain of the FSIQ-RMS from baseline up to EOS;• Longitudinal percent change over time in brain volume from baseline up to EOS;
--	--

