11 STATISTICAL METHODS

All statistical analyses will be conducted by Actelion or by designated CROs supervised by Actelion.

The Statistical Analysis Plan (SAP) will be approved prior to database lock for the final analyses. The SAP provides the full details of all analyses, data displays, and algorithms to be used for data derivations.

All data will be listed and endpoints will be summarized by appropriate descriptive statistics (tables or figures), typically including:

- Number of non-missing observations, number of missing observations, mean, standard deviation, median, Q1, Q3, minimum and maximum for continuous endpoints;
- Number of non-missing observations, number of missing observations and frequency with percentage per category (percentages based on the number of non-missing observations) for categorical endpoints;
- Number of subjects at risk, cumulative number of events, cumulative number of censored observations and Kaplan-Meier estimates of the survival function for time-to-event endpoints.

Absolute change from baseline is defined as post-baseline value minus baseline value, i.e., a positive sign indicates an increase as compared to baseline.

A percentage (relative) change from baseline is defined as the absolute change from baseline divided by the baseline value (if the baseline value does not = 0) multiplied by 100.

The baseline value for efficacy is defined as the last non-missing value recorded prior to randomization for each endpoint and each subject individually. The baseline value for safety is defined as the last non-missing value recorded prior to first study drug intake for each endpoint and each subject individually.

The EOS is defined as the date on the end-of-study eCRF page. If this date is missing the last recorded visit on the eCRF is considered as the EOS date.

The EOT date is defined as the date of the last dose of study treatment intake.

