The variables required for this endpoint are the visit identifier and the absolute change in the FSIQ-RMS fatigue-related symptoms at each visit defined as the value at each visit up to EOS minus the value at baseline. Additional details for dealing with missing data will be provided in the SAP.

11.2.2.5 Longitudinal percent change over time in brain volume (PCBV) from baseline up to EOS

PCBV will be calculated at each visit using the skull as scaling constraint by performing halfway registration between images from the MRI assessments from baseline up to EOS:

- Percent change from the mean brain surface displacement between the MRI scans (SIENA method).

Further details of the derivation of this variable will be provided in the SAP.

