11.3.3.5.2 Analyses

The primary analysis of percent change from baseline in brain volume will be performed on the FAS using an adjusted generalized linear mixed model using the same approach as for the FSIQ-RMS secondary endpoint above [Section 11.3.3.4.2].

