11.3.4 Analysis of the other efficacy variables

The analyses of all exploratory variables will be based on the FAS and described in detail in the SAP. If required, exploratory variables will also be analyzed by subgroups. Each null hypothesis will be tested with a two-sided significance level set to 0.05 in an exploratory manner. All statistical models used will be stratified by baseline EDSS category. For analyses by visit, the observed data will be used as primary analysis and a supportive analysis will use last observation carried forward (LOCF) or other imputation methods where appropriate.

11.3.4.1 Mean number of Gd+ T1, CUAL and new or enlarging T2 lesions by visit

The mean number of Gd+ T1, CUAL and new or enlarging T2 lesions per subject per scan up to Week 48, Week 96, Week 144, EOT and EOS will be analyzed using a negative binomial regression model similar to that described in Section 11.3.3.4.

11.3.4.2 Change in volume of T2 lesions, volume of T1 hypointense lesions and EDSS from baseline to each visit

All variables related to change in lesion volume and change in EDSS at Week 48, Week 96, Week 144, EOT and EOS will be analyzed using an analysis of variance

(ANOVA) with treatment, baseline EDSS category as covariate. Changes to other visits will be summarized descriptively.

11.3.4.3 Absence of Gd+ T1 lesions, absence of new or enlarging T2 lesions, absence of new T1 hypointense lesions and subjects relapse-free

Absence of Gd+ T1 lesions, new T1 hypointense and new or enlarging T2 lesions at Week 48, Week 96, Week 144, EOT and EOS will be analyzed using a logistic regression model with treatment as a factor, including baseline EDSS category as covariate. Subjects that are relapse-free at EOT + 30 days will be analyzed in a similar manner.

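### Protocol section 11.3.3.4.2 puts the FSIQ-RMS symptom test on percent change, although the endpoint and hypothesis are absolute change, and its primary model leaves out the baseline score

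*Protocol*

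**What the plan says.** All references are to the protocol.

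- The synopsis, under secondary endpoint variables, lists "Longitudinal absolute change over time in fatigue-related" symptoms from baseline to end of study.
- Section 11.2.2.4 defines the variable as "the absolute change in the FSIQ-RMS fatigue-related symptoms at each visit", that is, the visit value minus the baseline value.
- Section 11.3.3.4.1 gives the purpose of the model as "to compare the overall absolute change in the fatigue score between the two treatment groups" and says that this null hypothesis is tested by an F-test.
- Section 11.3.3.4.2, the primary analysis, says: "An F-test will be used to compare the overall mean percent change over time in ponesimod compared to placebo". Its model is an "adjusted generalized linear mixed model with treatment, time, baseline EDSS category as fixed effect", with subject as a random effect.
- Section 11.3.3.4.3 mentions additional baseline covariates only for a supportive model and does not name them.
- Section 11.3.3.5.2 analyses percent change in brain volume "using the same approach as for the FSIQ-RMS secondary endpoint above".
- Section 11 defines percent change only "if the baseline value does not = 0".
- Section 11.3.3 tests the five secondary endpoints in fixed order at two-sided 0.05 and stops at the first non-rejection. FSIQ-RMS symptoms stand fourth and brain volume fifth.

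**The concern.** The hypothesis section and the analysis section name the same F-test but apply it to different variables. A programmer who follows 11.3.3.4.2 literally answers a question other than the stated hypothesis. One who follows 11.3.3.4.1 departs from the text that specifies the primary analysis. For an endpoint inside the alpha-controlled sequence, one that also decides whether brain volume is tested, the test variable has to be fixed without ambiguity. The scale of the reported difference in treatment means and its confidence interval is left open in the same way.

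Percent change also suits this score poorly. The scale reaches 0, no eligibility criterion requires a minimum level of fatigue, and subjects with EDSS 0 may enter. Low baselines are therefore possible, and a baseline of 0 gives no value at all.

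The second part is separate. The model adjusts for EDSS category but not for the baseline value of the outcome, which section 7.2.6 collects before randomization.

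**Working it through.** **Is there a figure to reproduce?** No. Section 11.5 gives power only for the relapse rate and 12-week CDA. The protocol states no mean, SD, correlation or effect size for FSIQ-RMS. What follows on power and variance therefore uses assumed inputs.

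**1. Which scale?** Three places say absolute (synopsis, 11.2.2.4, 11.3.3.4.1). One says percent (11.3.3.4.2). Brain volume, where percent change is the endpoint (11.3.3.5.1), refers back to 11.3.3.4.2, so the word *percent* was probably carried over.

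**2. How percent change behaves on a 0–70 score.** Percent change = 100 × (follow-up − baseline) / baseline.

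- 2 to 8: 100 × 6/2 = +300%.
- 40 to 46: 100 × 6/40 = +15%.
- Baseline 0: undefined.

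The same 6-point worsening counts 20 times as much in the first subject as in the second. The score is averaged over 7 days, so a baseline below one point is possible. From 1/7 to 10 is 100 × (10 − 1/7)/(1/7) = +6,900%.

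**3. Illustrative power.** Simulation with 300 per arm (11.5.1), 2,000 replicates, normal scores truncated to 0–70, one follow-up value, two-sided 0.05. The additive effect was set for about 80% power on absolute change: effect = SD × √(2(1 − ρ)) × (1.96 + 0.8416) × √(2/300). For SD 10 and ρ = 0.5 this is 10 × 1 × 2.8016 × 0.08165 = 2.29 points.

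| Assumed baseline mean (SD) | ρ | Absolute | Absolute + baseline score | Percent | Baseline 0 |
|---|---|---|---|---|---|
| 40 (10) | 0.5 | 80.1% | 90.3% | 68.9% | 0% |
| 40 (10) | 0.7 | 81.4% | 87.5% | 72.9% | 0% |
| 30 (14) | 0.5 | 81.2% | 90.0% | 19.4% | 1.6% |
| 30 (14) | 0.7 | 80.7% | 85.8% | 25.5% | 1.6% |
| 25 (15) | 0.5 | 79.6% | 90.6% | 14.6% | 4.8% |
| 25 (15) | 0.7 | 78.7% | 83.9% | 18.4% | 4.8% |
| 20 (12) | 0.5 | 76.9% | 88.4% | 15.7% | 4.8% |
| 20 (12) | 0.7 | 79.1% | 85.2% | 18.0% | 4.8% |

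Percent change lost power in all eight settings. The loss is moderate when baselines are high and tight, and severe when they spread toward zero. The share at baseline 0 is the lower tail of the assumed normal distribution piled up at 0. It is not an estimate for this trial.

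**4. Cost of omitting the baseline score.** With equal variances and correlation ρ, one follow-up visit gives variance(adjusted) / variance(change score) = (1 + ρ)/2.

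- ρ = 0.5: 0.75, a cut of 25%.
- ρ = 0.7: 0.85, a cut of 15%.

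The planned model uses repeated visits. For the mean of m equally correlated visits, let p = (1 + (m − 1)ρ)/m. Then variance(change score) / variance(adjusted) = (p + 1 − 2ρ)/(p − ρ²).

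- m = 4, ρ = 0.5: p = 0.625; 0.625/0.375 = 1.67.
- m = 8, ρ = 0.5: p = 0.5625; 0.5625/0.3125 = 1.80.
- m = 4, ρ = 0.7: p = 0.775; 0.375/0.285 = 1.32.
- m = 8, ρ = 0.7: p = 0.7375; 0.3375/0.2475 = 1.36.

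Under these assumptions the single-visit figure understates the gain.

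**The case against.** The strongest reply is that the protocol does not adopt percent change. Three places, including the formal hypothesis, fix the absolute scale, and one stray word is easily recognised as such. This stands as far as intent goes: a reader might infer that the endpoint will be tested on the percent scale and lose most of its power, and the text does not support that. It does not remove the contradiction, because the odd word sits in the sentence that specifies the test. For this endpoint the protocol explicitly leaves missing data to the SAP; the scale and fixed effects are written here, so a SAP that picks one scale still departs from a protocol sentence.

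A second reply is that leaving out the baseline score is a matter of efficiency. This also stands. A reader might infer bias, but a randomized comparison of change scores is unbiased without the covariate, and a supportive model with further covariates is planned.

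A third reply limits the reach of the point, and it stands too. A reader might extend the covariate argument to other analyses, but the protocol does not support this:

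- **Brain volume:** SIENA derives percent change directly from pairs of scans, and section 7.2.3 does not list a baseline brain volume among the MRI variables.
- **Analyses of change in lesion volume, EDSS, MSFC and SDMT:** these are exploratory and left to the SAP (11.3.4). The EDSS model already contains baseline EDSS category.
- **Combined unique active lesions:** no defect in that model has been shown.

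**Conclusion.** The point holds in two parts of unequal weight. The contradiction between absolute and percent change in 11.3.3.4 is certain from the text and needs correcting before analysis, because it leaves the test variable of an alpha-controlled endpoint undecided. The missing baseline score is a loss of precision that is cheap to recover; its size depends on the assumed correlation.

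No power figure can be given for this trial. The spread in the simulation, from about 80% down to 69–73% in one case and to 15–26% in the others, comes from baseline means and SDs that the protocol does not give, and from a single follow-up value in place of the planned repeated-measures model. It supports the direction of the loss but not a specific size.

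**What to change.** - **Section 11.3.3.4.2:** replace *percent* with *absolute* in the F-test sentence, and add the baseline FSIQ-RMS symptom score as a continuous covariate in the primary model.
- **Section 11.3.3.5.2:** state that the brain-volume model uses the same structure (treatment, time, baseline EDSS category, random subject) with percent change as the outcome. Otherwise the cross-reference would point to an absolute-change analysis and import the fatigue covariate.
- **SAP:** carry the same wording.

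The cost is a change of text before unblinding. The baseline score is already collected. Change from baseline cannot be formed without it, so the covariate excludes no further subject.

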3.5.2 Treatment period

This period consists of a double-blind treatment period, which starts after randomization with the first dose of study treatment during Visit 3 (Day 1 of study).

The double-blind treatment period has a variable duration from a minimum of 60 weeks (for the last subject randomized) to a maximum of 156 weeks (3 years) for the first subjects randomized in the trial. Average duration is expected to be approximately 2 years. It includes a randomization visit, visits at 2, 4 and 12 weeks after randomization, and 12-weekly visits thereafter until 60 weeks after the randomization of the last subject or 156 weeks of treatment (whichever occurs first).

For an individual subject, this period starts on the day of the first study treatment intake and continues until the premature discontinuation of study treatment, Week 156, or until 60 weeks after the randomization of the last subject (whichever occurs first).

EOT visit: The EOT visit at an individual level should preferably take place 1 day after the last dose of study treatment, but no later than 7 days after the last dose of study treatment.

3.5.2.1 *Modification of treatment*

If a subject meets one of the following conditions:

- The subject has experienced a confirmed relapse while on study treatment;
- The subject has experienced an event of 24-week CDA while on study treatment;

Then, the principal investigator / treating neurologist should consider and propose the following options to this subject:

- Subject remains on study treatment. In this case, the subject will be asked to re-consent to continue receiving study treatment [see Section 13.3].
- Subject prematurely discontinues study treatment and DMF background therapy, and begins treatment with an approved MS therapy at the discretion of the treating neurologist in accordance with local practices. In this case, the subject will enter the post-treatment observation period (PTOP) of the study [see Section 3.5.3.2].

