3.5.4 Study duration

Assuming a subject recruitment time of 104 weeks (including the period from first subject, first visit [FSFV] to last subject, first visit [LSFV] and a 45-day pre-randomization period for the last randomized subject), the overall duration of the study from FSFV to last subject, last visit (LSLV) will consist of 104 weeks recruitment, followed by the minimum treatment time of 60 weeks, and 30 days post-treatment safety follow-up. This results in an anticipated study duration of approximately 168 weeks (3.3 years). The actual overall study duration or subject's recruitment period may vary.

For an individual subject, the maximum duration time will consist of a 45-day pre-randomization period followed by a maximal 156-week treatment period and a 30-day post-treatment safety follow-up. This results in a maximal total participation time of approximately 167 weeks (3.3 years).

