11.3.3.5.1 Hypothesis

The secondary endpoint percent change from baseline over time in brain volume up to EOS will be analyzed using a generalized linear mixed model to account for repeated measures, to compare the overall percent change in brain volume between the two treatment groups. The hypotheses are expressed as a linear combination of the fixed-effects and are tested at a two-sided significance level of 0.05:

$$H_0, \text{PCBV}: \mu_{\text{Ponesimod}} - \mu_{\text{Placebo}} = 0$$

vs

$$H_1, \text{PCBV}: \mu_{\text{Ponesimod}} - \mu_{\text{Placebo}} \neq 0$$

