11.5.1 Primary endpoint

The sample size for the study was determined by a simulation using the negative binomial distribution. A sample size of 600 subjects (300 per treatment group) will provide a power of approximately 90% for a significance level of 0.05, under the assumption that the ARR (for confirmed relapses up to EOS) is 0.50 for placebo and 0.325 for ponesimod (which corresponds to a risk reduction of 35%), and using a dispersion $k = 1.3$ (where the variance is $= \mu + k \mu^2$). A mean subject follow-up of 1.9 years is assumed with 3.3 years maximum follow-up.

The dispersion from the ponesimod Phase 2 study was 1.0; a higher dispersion is assumed here due to the potentially higher disease activity in this subject population.

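### Compound symmetry is the named covariance for the brain-volume test, with no rule for replacing it; if it is kept with the treatment-by-time term, the 5% test would run at roughly 8–20% under assumed variances

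*Protocol*

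**What the plan says.** Protocol 11.3.3.4.2 sets the primary analysis of the FSIQ-RMS symptom score. The listed fixed effects are treatment, time and baseline EDSS category, with "subject as a random effect". The section then says that the visit differences, the time effect and "the interaction between treatment and time will be assessed within the same model". On covariance it says: "The compound symmetry covariance matrix will be used in the model, however the suitability of this structure will be assessed visually". The rest of that sentence adds a comparison with an unstructured or autoregressive matrix by Akaike's information criterion (AIC). It does not say what happens to the primary analysis if either check speaks against compound symmetry, or if the two checks disagree.

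Section 11.3.3.5.2 analyses percent change in brain volume "using the same approach as for the FSIQ-RMS secondary endpoint above". Section 11.3.3.5.1 says its hypotheses "are tested at a two-sided significance level of 0.05". Section 11.3.3 places brain volume fifth and last in the secondary hierarchy.

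The design facts that matter here are scans every 24 weeks to Week 144 (7.2.3) and a treatment period of "variable duration from a minimum of 60 weeks (for the last subject randomized) to a maximum of 156 weeks" (3.5.2).

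**The concern.** Compound symmetry assumes one variance at every visit and one correlation between all visits. Percent change in brain volume is measured from a single baseline scan. If subjects lose volume at different rates, its spread widens with time. Because follow-up is staggered, the widest-spread visits also hold the fewest subjects. A pooled variance then overstates the standard error at early visits and understates it at late ones. An overall contrast that weights the visits equally inherits the late-visit understatement.

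Two gaps leave this open. The AIC comparison has no stated consequence, so compound symmetry can stay primary whatever it shows. And the list of fixed effects has no interaction, while the next sentences need one in the same model, so the reader cannot tell which model yields the confirmatory F-test. The choice decides whether that test holds its level. At stake is a false claim on brain volume and misleading visit-wise intervals.

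**Working it through.** **Inputs from the protocol.** Two-sided 0.05 (11.3.3.5.1); 300 per arm (11.5.1); scans at Weeks 24, 48, 72, 96, 120 and 144 (7.2.3); follow-up 60–156 weeks (3.5.2). Section 3.5.4 begins "Assuming a subject recruitment time of 104 weeks", and that includes a 45-day pre-randomization period. Randomization therefore spans about 104 − 45/7 = 97.6 weeks, and 60 + 97.6 ≈ 158, so uniform follow-up over 60–156 weeks is a fair approximation.

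**Inputs assumed, because the protocol has none.** Between-subject slope SD σs = 0.2–0.6 %/year; shared baseline-scan error SD σb = 0.2–0.4 %; residual SD σe = 0.2–0.4 %; dropout 0–20% at 2 years.

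**Who is left.** The share reaching week w is min[1, (156 − w)/96]. At Week 96 this is 60/96 = 0.625. At Week 144 it is 12/96 = 0.125, or 37.5 of 300 per arm before dropout.

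**How the variance grows.** Var(t) = σs²t² + σb² + σe², with t in years (Week 24 = 0.46, Week 144 = 2.76). With all three SDs at 0.4:
- Week 24: 0.16 × 0.212 + 0.32 = 0.354
- Week 144: 0.16 × 7.62 + 0.32 = 1.539

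The variance rises more than fourfold. Fitting compound symmetry to this pattern with 10% dropout gives one variance of about 0.60 (0.23 residual + 0.365 shared) for all visits.

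**Check on the stated level.** If compound symmetry is true, the same calculation under staggered follow-up and 10% dropout returns a size of 0.0500, which reproduces the protocol's 5%.

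**Size when compound symmetry is wrong but kept.** The model has treatment-by-visit terms and the tested contrast is the equal-weight mean of the six visit differences. With r = model-based SE / true SE, size = 2[1 − Φ(1.96 r)]. For the setting above, r = 0.761, so size = 2[1 − Φ(1.491)] = 13.6%.

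Results with 10% dropout; the simulations used 2,000 trials per setting under no treatment effect:

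| σs / σb / σe | r | Size, large-sample | CS, simulated | AR(1), simulated | Unstructured, simulated | Week 144 coverage under CS |
|---|---|---|---|---|---|---|
| 0.2 / 0.4 / 0.4 | 0.88 | 8.5% | 8.4% | 10.8% | 4.6% | 89% |
| 0.4 / 0.4 / 0.4 | 0.76 | 13.6% | 13.6% | 13.1% | 5.7% | 81% |
| 0.4 / 0.2 / 0.2 | 0.68 | 18.3% | 18.2% | 13.2% | 5.4% | 71% |
| 0.6 / 0.2 / 0.2 | 0.66 | 19.7% | 21.4% | 16.0% | 5.6% | 66% |

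CS is compound symmetry and AR(1) is first-order autoregressive. The simulation standard error near 5% is √(0.05 × 0.95/2000) ≈ 0.5 points, so the unstructured column is consistent with 5%.

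**What the result depends on.**
- Dropout: large-sample size is 8.2–18.2% with none and 8.8–21.5% with 20%.
- End-of-treatment scans mapped to the nearest 24-week visit: 7.5–14.7%.
- Complete 144-week data: 5.0% for the overall test, but Week 144 coverage is still only 80–90%.
- Compound symmetry with no interaction term: 5.0% in every setting.
- Week 24 coverage under compound symmetry is 96–100%, so those intervals are too wide.
- AIC across the three structures chose unstructured in 1,994 of 2,000 trials in the mildest setting and in all 2,000 in each of the others. Following AIC gave 4.6–5.7%.

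**The case against.** The strongest reply is that the protocol does not commit to compound symmetry regardless. Its sentence continues to an AIC comparison, and with growing variance AIC picks unstructured almost every time, with size near 5%. That stands as far as it goes: the inflation arises only if the check is not acted on. But nothing says it will be. The visual check may disagree with AIC, and one of the two named alternatives, autoregressive, is itself anti-conservative here. If the sponsor means to follow AIC, naming unstructured now loses nothing.

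Second, the listed fixed effects contain no interaction, and that model holds 5.0%. This also stands. But separate visit differences and an interaction cannot come from a model without a treatment-by-time term, so the text supports both readings.

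Third, the protocol states no visit weighting, and its hypothesis is the overall difference; brain-volume change at named weeks is exploratory (6.1.3). The interval problem at single visits is therefore not a confirmatory error.

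Fourth, the SAP may settle this. Convergence and degrees-of-freedom details do belong there and are not criticised. The named structure and the tested model are what the protocol itself fixes or leaves contradictory.

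Finally, the random subject effect alongside compound symmetry can be read as one structure described twice. No harm to inference from it was shown.

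**Conclusion.** The point holds as a conditional one. Compound symmetry is a poor named default for brain volume, no rule replaces it, and the model behind the confirmatory test is ambiguous. If it is kept with the interaction and equal visit weights, size is roughly 8–20% (up to about 21% in the most extreme simulated setting), and Week 144 intervals cover about 66–90%. This rests on assumed variance components and on staggered follow-up.

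A reader might infer that the plan's brain-volume test has an 8–20% error rate as a matter of fact. The documents do not support that: the AIC step, if followed, and the main-effects model both give about 5%. Nor do they support extending the figure to FSIQ-RMS, which shares the wording but for which no growth in variance was shown, or to the rest of the hierarchy. Brain volume is tested last, only after every earlier hypothesis is rejected, and nothing follows it.

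**What to change.** In 11.3.3.4.2 and 11.3.3.5.2:
- Name unstructured covariance as the primary structure.
- List the treatment-by-visit term among the fixed effects, and state the contrast, with its visit weights, that tests the null hypothesis.
- Replace the visual and AIC choice with a fixed fallback for non-convergence that uses sandwich standard errors. In separate simulations (1,200 trials in each of three other variance settings, 8% dropout per year), compound symmetry with sandwich errors gave 4.2–4.7%. Autoregressive covariance with model-based errors should not be the fallback.
- Drop the separate random subject effect, which an unstructured matrix makes redundant.
- Keep compound symmetry, if wanted, as a sensitivity analysis.

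The cost is wording only. Six visits need 6 × 7/2 = 21 covariance parameters, which 600 subjects support easily. Late-visit intervals will be somewhat wider, because they will reflect the true spread at those visits.
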